## 1 INTRODUCTION

The purpose of this statistical analysis plan (SAP) is to describe the statistical methods, data derivations and data summaries that will be used to analyze and report results for Protocol BIO89-100-221 Version 3.0.

The SAP will supersede the protocol in the event of any differences between the two documents in the plans for data analysis, and the protocol will be amended if appropriate. The SAP will be included as an appendix in the clinical study report.

## 2 STUDY OBJECTIVES

This Phase 2 study is designed to evaluate the efficacy, safety, and tolerability of different doses and dose regimens (every week [QW] or every 2 weeks [Q2W]), subcutaneous (SC) dosing of BIO89-100 compared to placebo in subjects with Severe Hypertriglyceridemia (SHTG).

### 2.1 PRIMARY OBJECTIVE

The primary objective is to determine the effect of BIO89-100 on serum Triglycerides (TG) levels in subjects with SHTG (TG  $\geq$ 500 mg/dL).

### 2.2 SECONDARY OBJECTIVES

The secondary objectives of the study are:

- To determine the effect of BIO89-100 on selected serum lipids and lipoproteins
- To determine the effect of BIO89-100 on high sensitivity C-reactive protein (hsCRP)
- To determine the effect of BIO89-100 on metabolic markers
- To characterize BIO89-100 pharmacokinetics (PK)
- To characterize BIO89-100 pharmacodynamic (PD) profile as assessed by Magnetic Resonance Imaging – Whole Liver Proton Density Fat Fraction (MRI-PDFF)

### 2.3 OTHER OBJECTIVES

The other objectives of the study are:

- [REDACTED]
- [REDACTED]

The safety objectives of the study are:

- To evaluate the safety and tolerability of BIO89-100
- To determine the effect of BIO89-100 on [REDACTED]
- Other safety assessments

### 3 STUDY DESIGN

### 3.1 STUDY POPULATION

[figure not shown]
Study BIO89-100-221 is a randomized, double-blind, placebo-controlled, Phase 2 study to evaluate the efficacy, safety, tolerability, PK and PD profiles, and [REDACTED] of BIO89-100 administered QW or Q2W SC for 8 weeks and followed by a 4-week follow-up period.

The main cohort will include approximately 90 subjects with SHTG without concurrent fibrate therapy and will consist of 5 treatment groups to compare 4 dose levels/regimens of BIO89-100 versus placebo (Figure 1). The fibrate expansion cohort will include approximately 36 subjects with SHTG on stable background fibrate therapy and with a baseline MRI-PDFF  $\geq 6\%$  and will consist of 2 treatment groups comparing one dose regimen of BIO89-100 versus placebo (Figure 2).

[figure not shown]
The study includes Lifestyle Stabilization, TG Qualification, Treatment, and Follow-up periods.

### 3.2 DOSAGE AND ADMINISTRATION

Subjects enroll in the main cohort will be dosed with one of four doses of BIO89-100 (9 mg QW, 18 mg QW, 27 mg QW, or 36 mg Q2W) or placebo. The subjects enroll in the fibrate expansion cohort will receive BIO89-100 27 mg or placebo QW. Intensive PK is planned for a subset of subjects (optional participation with no more than 45 subjects).

### Figure 1. Study Schema: Main Cohort

**Figure 2. Study Schema: Fibrate Expansion Cohort**

### 3.3 BLINDING AND RANDOMIZATION METHODS

Eligible subjects will be randomized in the order they are enrolled into the study. Subjects in the main cohort will be randomized in a 1:1:1:1 ratio to 1 of 4 doses of BIO89-100 (9 mg QW, 18 mg QW, 27 mg QW, or 36 mg Q2W) or placebo. Subjects in the fibrate expansion cohort will be randomized in a 1:1 ratio to BIO89-100 27 mg or placebo QW.

[REDACTED]

[REDACTED]

Randomization in the main cohort will be stratified by TG <750 mg/dL or ≥750 mg/dL (8.47 mmol/L) and by whether or not the subject is receiving background therapy (e.g., prescription fish oil and/or statins). [REDACTED]

[REDACTED] All subjects will be centrally assigned to randomized IP using an Interactive Voice/Web Response System (IVRS/IWRS). Before the study is initiated, the log-in information and directions for the IVRS/IWRS will be provided to each site.

The study will be conducted under double-blind conditions. The subjects, PI, other study personnel involved with subject assessments, and 89bio will remain blinded to the actual treatment assignments of the subjects, post-baseline lipid panels (Triglycerides [TG], [REDACTED] [REDACTED], Low Density Lipoprotein Cholesterol [LDL-C], High Density Lipoprotein Cholesterol [HDL-C], Non-high Density Lipoprotein Cholesterol [Non-HDL-C], Very Low Density Lipoprotein Cholesterol [VLDL-C], Very Low Density Lipoprotein Triglycerides [VLDL-TG], [REDACTED], Apolipoprotein B100 [ApoB]), [REDACTED], Remnant Lipoprotein Cholesterol [RPL-C], [REDACTED] [REDACTED], and PK data. Blinded IP will be provided by a clinical supplies vendor and shipped to the study site. IP may be delivered to the subject's home for home administration by an HHP. The SC administration of the blinded IP will be performed by trained study staff, and only blinded staff will be involved with subject assessments.

### 3.4 STRATIFICATION FACTORS

Randomization in the main cohort will be stratified by (i) TG <750 mg/dL or  $\geq$ 750 mg/dL (8.47 mmol/L) and (ii) whether the subject is receiving background therapy (e.g., prescription fish oil and/or statins) – Yes / No. [REDACTED]

[REDACTED]

### 3.5 SAMPLE SIZE CONSIDERATIONS

The effect of BIO89-100 on the percentage change from baseline in TG is estimated based on prior clinical studies evaluating BIO89-100 and other triglyceride lowering agents. [REDACTED]

[REDACTED]

[REDACTED]

[REDACTED]

[REDACTED]

[REDACTED]

[REDACTED]

[REDACTED]

[REDACTED]

Based on these results, it is estimated that the SD of the percent change in TG at Week 8 is approximately 40%. With 18 subjects in the placebo group and each BIO89-100 active treatment group, there would be at least 86% power to detect a 45% difference in TG between each BIO89-100 active treatment group and placebo at the 2-sided alpha level of 0.05, assuming 50% reduction in BIO89-100 dose group and 5% in the placebo group. This sample size assessment incorporates approximately 10% of subjects will be lost to follow-up.

Approximately 90 subjects are planned to be enrolled in the main cohort, with 18 subjects in each of the BIO89-100 active treatment groups (9 mg QW, 18 mg QW, 27 mg QW, or 36 mg Q2W) and in the placebo group. The study aims to enroll ~33% of subjects (~30 subjects total) in the main cohort with a baseline MRI-PDFF  $\geq$  6%. Approximately 36 subjects are planned to be enrolled in the fibrate expansion cohort (18 in each treatment group) with all subjects having baseline MRI-PDF  $\geq$  6%. Subjects who terminate early in either cohort may be replaced at Sponsor's discretion.

### 3.6 INTERIM ANALYSIS

No efficacy interim analysis is planned for this study.

### 3.7 DATA MONITORING COMMITTEE

No data monitoring committee is planned for this study.

## 4 STUDY ENDPOINTS AND COVARIATES

## 4.1 PRIMARY EFFICACY ENDPOINT

- Percentage change in serum TG from baseline to Week 8

## 4.2 SECONDARY EFFICACY ENDPOINTS

- The proportion of subjects who achieve TG < 500 mg/dL at Week 8
- Percentage change in VLDL-C, LDL-C, non-HDL-C, HDL-C, VLDL-TG, ApoB, remnant lipoprotein cholesterol (RLP-C), hsCRP from baseline to Week 8
- Percentage change in fasting plasma glucose, adiponectin, and body weight from baseline to Week 8
- The serum BIO89-100 concentrations and PK parameters
- Percentage change and change from baseline in hepatic steatosis using Magnetic Resonance Imaging – Whole Liver Proton Density Fat Fraction (MRI-PDFF)

### 4.3 OTHER EFFICACY ENDPOINTS

• [REDACTED]

## 4.4 SAFETY ENDPOINTS

### 4.4.1 Adverse Events

The evaluation of adverse events (AE) will include only incidence of treatment-emergent AEs (TEAEs), defined as AEs with onset date and time after or identical to the date and time of the first dose of the investigational product until the last dose + 28 days or continuing AEs that worsen the grade post IP. When onset time is missing or partial missing, AE occurs on the same day as first dose date are considered as TEAE. The frequency of TEAEs, treatment-emergent serious AEs (TESAEs), and number of subjects who discontinue due to TEAEs will be summarized.

### 4.4.2 Clinical Safety Laboratories

The evaluation of clinical safety laboratories, including blood hematology, chemistry, 24-hour urine cortisol, and urinalysis will be based on the observed values. Observed values and changes from baseline will be summarized for all post-baseline study visits.

Incidence and shifts of laboratory abnormalities will be summarized.

Changes in liver function tests (i.e., alkaline phosphatase (ALP), alanine aminotransferase (ALT), aspartate aminotransferase (AST), albumin and Gamma-Glutamyl Transferase (GGT)) from baseline to Week 8 will be summarized. A summary of suspected liver injury cases according to drug induced liver injury (DILI) criteria will also be presented ([Table 1](#)).

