#### 2.2.3. BIO89-100

BIO89-100 is a glycoPEGylated analog of FGF21 that has an N-terminal methionine residue, 2-point mutations, and a single 20 kDa linear PEG covalently attached via a glycosyl moiety. Both point mutations are less likely to be exposed due to steric hindrance by the PEG domain, and thereby less likely to trigger an immune response. It has been evaluated in non-clinical pharmacology, PK, and toxicology studies and in a recently-completed, first-in-human, single ascending dose (SAD) study (TV47948-SAD-10122).

[figure not shown]
TV47948-SAD-10122, a Phase 1, first-in-human, randomized, double-blind, placebo-controlled study to evaluate the safety, tolerability, and PK properties of BIO89-100 following SC administration of SAD, has recently been completed.

No significant safety issues have been identified. The most common reported AEs (≥2 in the pooled BIO89-100 group) were injection site reactions (all common terminology criteria for adverse events [CTCAE] Grade 1), headache, contact dermatitis, and nausea. There were no deaths, SAEs, or discontinuations, and review of ECG, clinical laboratories, and vital sign data did not reveal any concerning trends. There was a single CTCAE Grade 3 TEAE that was considered not treatment-related (elevated creatine phosphokinase level at EOS in a physical laborer). No other CTCAE Grade 3 or above TEAE was reported.

Part 1 of BIO89-100-002 is a randomized, double-blind, placebo-controlled, multiple ascending dose (MAD) study to evaluate the safety, tolerability, PK and PD profiles, and BIO89-100 administered SC in subjects with NASH or with NAFLD who are at a high risk of NASH. Subjects were treated at QW SC doses of 3 mg, 9 mg, 18 mg, and 27 mg, and Q2W SC doses of 18 mg and 36 mg of BIO89-100 or placebo. Data from the MAD study Part 1 demonstrated favorable safety and tolerability with repeated dosing of BIO89-100 for 12 weeks with evidence of clinical efficacy in NASH (clinically meaningful reductions in liver fat assessed by MRI-PDFF and in ALT).

A detailed description of the chemistry, pharmacology, efficacy, and safety of BIO89-100 is provided in the Investigator's Brochure (IB).

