## 6.8.1. Monitoring and Discontinuation for Suspected Drug-induced Liver Injury (DILI) Criteria

A subject will be additionally monitored if they meet any of the following liver-related criteria. Baseline value is defined as the last ALT and AST values performed prior to or on the

New transaminase elevations in subjects with baseline value within the normal range:

For new elevations in transaminases greater than 2× ULN, repeat measurement should be performed within 48 to 72 hours. If elevations persist, subjects should be evaluated for other causes of transaminase elevations and with tests of hepatic function. If no other cause is identified, then the subjects need to be monitored closely (see below), and discontinuation of the study drug should be considered.

Drug should be discontinued, and the subject followed until resolution of symptoms or signs in the following situations:

- ALT or AST >8× ULN
- ALT or AST >5× ULN for more than 2 weeks
- ALT or AST  $>3 \times$  ULN and (TB  $>2 \times$  ULN or INR >1.5)
- ALT or AST >3× ULN with the appearance of fatigue, nausea, vomiting, right upper quadrant pain or tenderness, fever, rash, and/or eosinophilia (>5%)

New transaminase elevations in subjects with baseline ALT or AST > ULN:

For new elevations in transaminases greater than 2× baseline value or total bilirubin >1.5× ULN, repeat measurement should be performed within 48 to72 hours. If elevations persist, subjects should be evaluated for other causes of transaminase elevations and with tests of hepatic function. If no other cause is identified, then the subjects need to be monitored closely (see below), and discontinuation of the study drug should be considered.

Drug should be discontinued and the subject followed until resolution of symptoms or signs in the following situations described in Table 3:

Table 3: Discontinuation Criteria in Subjects with Abnormal Baseline ALT or AST Values

| Baseline value of ALT/AST | Criteria to discontinue investigational product  |
|---------------------------|--|
| <2× ULN                   | if ALT or AST increases to >5× baseline value  |
| ≥2× ULN but <5× ULN       | if ALT or AST increases to >3× baseline value  |
| ≥5× ULN                   | if ALT or AST increases to >2× baseline value  |

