| Other                     | if ALT or AST increase >2× baseline value AND the increase is accompanied by a concomitant total bilirubin increase to >2× ULN OR the INR concomitantly increases by >0.2                          |
|                           | if ALT or AST increase >2× baseline value in the presence of signs and symptom(s) such as fatigue, nausea, vomiting, right upper quadrant pain or tenderness, fever, rash, and/or eosinophil (>5%) |

ALT = alanine aminotransferase; AST = aspartate aminotransferase; INR = International Normalized ratio; ULN = Upper limit of normal

Close monitoring for suspected DILI includes:

- Repeating liver enzyme and serum bilirubin tests 2 or 3 times weekly. Frequency of repeat testing can decrease to once a week or less if abnormalities stabilize or the trial drug has been discontinued and the subject is asymptomatic.
- Obtaining a more detailed history of symptoms and prior or concurrent diseases.
- Obtaining a history of concomitant drug use (including non-prescription medications and herbal and dietary supplement preparations), alcohol use, recreational drug use, and special diets.
- Ruling out acute viral hepatitis types A, B, C, D, and E, autoimmune or alcoholic hepatitis, hypoxic/ischemic hepatopathy; and biliary tract disease.
- Obtaining a history of exposure to environmental chemical agents.
- Obtaining additional tests to evaluate liver function, as appropriate (e.g., INR, direct bilirubin).
- Considering gastroenterology or hepatology consultations.

Note: If a subject lives in a remote area, laboratory testing can be performed locally, and the results should be promptly communicated to the Investigator site.

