**Table 1. Suspected liver injury cases according to drug induced liver injury (DILI) criteria**

Baseline Value of ALT/AST	Criteria to discontinue investigational product
>ULN and <2× ULN	ALT or AST >5× baseline value
≥2× ULN but <5× ULN	ALT or AST >3× baseline value
≥5× ULN	ALT or AST >2× baseline value
>ULN	ALT or AST >2× baseline value and (BILI >2× ULN OR INR >0.2)
Within Normal Range	ALT or AST >8× ULN
	ALT or AST >5× ULN
	ALT or AST >3× ULN and (BILI >2× ULN or INR >1.5)

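### SAP Table 1, the basis of the suspected liver-injury summary, does not match the stopping criteria in Protocol 6.8.1: two symptom/eosinophilia criteria are absent and two other rows are altered.

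*SAP*

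**What the plan says.** Protocol 6.8.1 sets stopping criteria by baseline ALT/AST. For a normal baseline it states "Drug should be discontinued, and the subject followed until resolution of symptoms or signs in the following situations" and gives four. The fourth is "ALT or AST >3× ULN with the appearance of fatigue, nausea, vomiting, right upper quadrant pain or tenderness, fever, rash, and/or eosinophilia (>5", where the 5 is a percentage. For an abnormal baseline, Protocol Table 3 has three criteria tiered by baseline level and two more under Other. One of those two is "if ALT or AST increase >2× baseline value AND the increase is accompanied by a concomitant total bilirubin increase to >2× ULN", with an INR increase above 0.2 as the alternative to bilirubin. The second is "if ALT or AST increase >2× baseline value in the presence of signs and symptom(s) such as fatigue, nausea, vomiting", and its list runs on to eosinophils above 5%.

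SAP 4.4.2 says "A summary of suspected liver injury cases according to drug induced liver injury (DILI) criteria will also be presented" and refers to SAP Table 1. That table's criteria column is headed as the criteria for stopping investigational product. It has seven rows and ends, for a normal baseline, with "ALT or AST >3× ULN and (BILI >2× ULN or INR >1.5". No redaction mark appears in it. SAP section 1 says the SAP prevails over the protocol where their analysis plans differ.

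**The concern.** The table carries the heading of the stopping rule, so a reader will take a subject counted in it as someone who met 6.8.1, and a subject not counted as someone who did not. Neither inference is safe. Because the SAP governs the analysis, the shorter and altered list is what would be programmed. This is the only visible summary in either document that applies the liver-injury criteria, and the trial has no data monitoring committee. At stake is whether the table can be reconciled with the subjects whose treatment was stopped under 6.8.1.

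**Working it through.** No sample-size or power figure is involved, so the check is a row-by-row comparison followed by worked cases.

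**Comparison**

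| Baseline ALT/AST | Protocol 6.8.1 | SAP Table 1 |
|---|---|---|
| Normal | >8x ULN | Same |
| Normal | >5x ULN lasting more than 2 weeks | >5x ULN, no duration |
| Normal | >3x ULN with bilirubin >2x ULN or INR >1.5 | Same |
| Normal | >3x ULN with symptoms and/or eosinophils >5% | Absent |
| >ULN, <2x ULN | >5x baseline | Same |
| 2x to <5x ULN | >3x baseline | Same |
| 5x ULN or more | >2x baseline | Same |
| >ULN | >2x baseline with bilirubin >2x ULN or INR rise >0.2 | INR printed as >0.2, not as a rise |
| >ULN | >2x baseline with symptoms and/or eosinophils >5% | Absent |

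The protocol has 4 + 5 = 9 criteria and the SAP has 3 + 4 = 7. The two absent criteria share their ALT/AST multiples (>3x ULN, >2x baseline) with the retained bilirubin/INR criteria. Below a baseline of 5x ULN, they are the only criteria that act at those multiples without a bilirubin or INR abnormality.

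**Worked cases** (assumed: bilirubin 0.7x ULN, INR 1.0 and unchanged)

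1. *Missed, normal baseline.* ALT 4x ULN with nausea. Protocol: 4 > 3 with a symptom, so met. SAP: 4 is not >8 and not >5; 4 > 3, but bilirubin and INR are normal, so no row is met.
2. *Missed or counted, abnormal baseline.* Baseline 1.5x ULN, ALT 6x ULN, with vomiting. 6/1.5 = 4x baseline. Protocol: 4 > 2 with a symptom, so met. SAP: 4 is not >5. The remaining row turns on INR. Read as a rise, 0 is not >0.2 and the subject is missed; if INR was not measured, the subject is also missed. Read literally, 1.0 > 0.2 and the subject is counted by accident.
3. *Over-counted, normal baseline.* A single ALT of 6x ULN, not sustained, no symptoms. Protocol: not met. SAP: 6 > 5, so counted.
4. *Over-counted, abnormal baseline, literal INR.* Baseline 1.5x ULN, ALT 4.5x ULN (3x baseline), no symptoms. Protocol: not met. SAP: 3 > 2 and 1.0 > 0.2, so counted.

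**Ranges.** Both rule sets were coded and run over on-study ALT from 0.5 to 20x ULN in steps of 0.1, with symptoms and two-week persistence each present or absent.

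- Normal baseline: protocol met but no SAP row at >3x to 5x ULN, under every reading of the INR term. Counted by the SAP only at >5x to 8x ULN.
- Baseline >ULN to <2x ULN: missed at >2x to 5x baseline (at 1.5x ULN, from >3x to 7.5x ULN), if INR is read as a rise or was not measured.
- Baseline 2x to <5x ULN: missed at >2x to 3x baseline (at 2.5x ULN, from >5x to 7.5x ULN), on the same condition.
- Baseline 5x ULN or more: nothing missed.
- Under the literal INR reading the abnormal-baseline gaps close, and the same ranges become over-counts for subjects without symptoms.

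An unmeasured INR is realistic: footnote f to the schedule in SAP Appendix 1 limits the coagulation panel to certain visits.

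**Size of one case.** 1/18 = 5.6 points; 1/36 = 2.8; 1/90 = 1.1. SAP 5.5 pools the cohorts, so on planned numbers (Protocol Table 1) 18 applies only to 9 mg, 18 mg and 36 mg. Placebo and 27 mg have 36 each, and pooled BIO89-100 has 18 + 18 + 36 + 18 = 90. SAP 5.5 reports low fibrate-cohort enrolment, so the real pooled denominators will be smaller than these.

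**The case against.** The strongest defence is that the table sits under clinical safety laboratories and was meant to be laboratory-only. That is a plausible design, but the SAP does not say so, the column heading says otherwise, and it would not explain leaving out eosinophils. The differential, in per cent, is in the hematology panel of SAP 7.6.2.

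Second, an affected subject is not lost to the report. Discontinuation reasons (SAP 7.2), adverse events leading to discontinuation (7.6.1) and laboratory shifts (7.6.2) may still show that subject. This stands and confines the problem to one table, but none of those outputs applies the liver-injury criteria. The table shells are in a separate document, so a clarifying footnote there cannot be ruled out.

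Third, the symptom list in Protocol Table 3 is open-ended and calls for judgement, so a programmed version can only approximate it. That also stands.

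A reader might go further and infer three things that the documents do not support:

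- *That the table under-counts.* The omission alone can only lower the count, but the lost duration and the INR wording can raise it.
- *That the omitted criteria have the lowest ALT thresholds.* They are joint lowest with the retained bilirubin/INR criteria.
- *That they would often be met because the first-in-human study listed "headache, contact dermatitis, and nausea" among its common events.* That was a single-dose study in which common meant two or more events in the pooled active group. It says nothing about nausea coinciding with a raised ALT.

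**Conclusion.** The mismatch is real. SAP Table 1 will not identify the subjects who meet Protocol 6.8.1. The normal-baseline gap, above 3x and up to 5x ULN with a symptom or eosinophilia, rests on no reading of the INR term. The abnormal-baseline gaps hold only if INR is read as a rise or was not measured. The net direction of error is undetermined. The documents give no event rate, so the number of misclassified subjects cannot be stated. This is a descriptive safety table, so the consequence is for its interpretation and reconciliation, not for any efficacy conclusion.

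**What to change.** Reconcile SAP Table 1 with Protocol 6.8.1 in every mismatched row, not only by adding rows:

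- Add the two symptom/eosinophilia criteria. Take eosinophils from the differential, and symptoms from coded adverse events within a pre-specified window around the ALT/AST sample, using a pre-specified preferred-term list.
- Align the INR term (rise or absolute value) and the duration on the >5x ULN row, and state how an unmeasured INR is handled.
- Cross-check the resulting cases against subjects discontinued for suspected drug-induced liver injury, and list any who appear in only one of the two. This also covers the judgement that a term list cannot capture.

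As a minimum, label the table laboratory-only, change its column heading, and report symptom-criterion cases beside it; the INR and duration terms still need aligning.

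The cost is SAP wording, a short preferred-term list and one extra derivation from data already collected. Counts may move in either direction. Trial conduct does not change, and no view is taken on which clinical rule is right; the two documents need to agree.
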